
Group 1. Basal bolus with glargine U300 once daily and glulisine insulin before meals (n=90).

Group 2. Basal bolus with glargine U100 once daily and glulisine insulin before meals (n=90).

IV.d. Basal Bolus Insulin Protocol.

Patients will be treated with a basal bolus insulin regimen as previously reported (15, 16, 39). In brief, subjects treated with insulin prior to admission will receive 80% of the total daily outpatient insulin dose given. Insulin naïve patients will discontinue oral agents and will receive a starting total daily dose (TDD) of 0.4 U/kg/day for BG between 140 mg/dl and 200 mg/dL and 0.5 U/kg/day for BG between 201 mg/dl and 400 mg/dL. The starting TDD will be reduced to 0.3 U/kg/day in patients \geq 70 years or with a GFR < 60 ml/min. Both groups will be treated with bolus regimen given half of TDD as basal (glargine U300 or U100) once daily and half as insulin glulisine divided in three equal doses before meals. Patients with poor oral intake or to be kept NPO will receive the basal dose, but prandial dose will be held (32). Insulin dose will be adjusted daily to maintain a fasting and pre-dinner BG between 80 mg/dl and 180 mg/dl.

IV. e Treatment randomization. This is an open label randomized controlled trial. Patients will be randomized 1:1 consecutively using a computer generated randomization table provided by [name], statistician at the Emory School of Public Health. The randomization table will be mailed to the research pharmacist at each institution who will be in charge of the randomization and group assignment. A research pharmacist at each institution will follow a computer-generated block randomization table based on prior insulin use (yes/no).

IV.f TREATMENT PROTOCOL - Basal Bolus Insulin Regimen with Glargine Once Daily plus Glulisine before Meals

Patients Treated with Insulin Prior to Admission

- Discontinue oral antidiabetic drugs on admission.

Subjects treated with insulin prior to admission will receive 80% or 100% of the total daily dose (TDD) given as basal bolus regimen. **Starting Insulin Doses:**

- Randomization BG <200mg/dl-give 80% of the TDD*
- Randomization BG>200mg/dl-give 100% of the TDD*
- Half of TDD will be given as basal (glargine U300 or U100) and half as rapid-acting insulin.
- Glargine U300 and U100 will be given once daily, at the same time of the day.
- Patients will receive the full-dose of glargine (even if NPO) the day of surgery or diagnostic procedure(s).

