V. Aim 2: To determine differences in glycemic control after hospital discharge between treatment with glargine U300 and glargine U100 in medicine and surgery patients T2D.

[figure not shown]
V.a. Rationale. Few studies have addressed the efficacy of insulin alone or in combination with oral agents after hospital discharge. In a recent study (see preliminary results section), patients were discharged on a combination of OADs and glargine U100 insulin or on a basal bolus regimen according to bA1c levels and achieved a marked reduction in HbA1c from 8.75% on admission to 7.9% and 7.35% after 4 and 12 weeks of hospital discharge. However, the use of glargine U100 alone or in combination to oral agents or as basal bolus insulin resulted in 30% and close to 40% incidence of hypoglycemia, respectively. In this study, we will compare the efficacy and safety of glargine U300 and U100 after hospital discharge. The total duration of the study is 3 months. Several outpatient insulin trials have shown that treatment with glargine U300 results in similar improvement in glycemic control, but in significant reduction in hypoglycemia compared to glargine U100 (23-27). Thus we expect that glargine U300 will be a safer alternative to current use of glargine U100 formulation.

V.b Insulin Discharge algorithm:

Patients with poorly controlled diabetes ($HbA1c \geq 7.5\%$) enrolled in Aim 1 will be invited to participate in this open label prospective outpatient study. The total duration of the study is 3 months.

- Patients with admission Hba1c < 7.5% will be discharged on their preadmission antidiabetic regimen and will not be included in the Aim 2 outpatient study.
- Patients with no previous pharmacological treatment prior to admission will be discharged on 50% of daily basal insulin (glargine U300 or glargine U100) hospital dose.
- Patients on oral agents prior to admission with an HbA1c between 7.5% and <10% will be discharged on oral agents plus glargine U300 or glargine U100 at 50% of the daily hospital dose.
- Patients on oral agents prior to admission with an admission A1C ≥ 10% will be discharged on their oral agents plus glargine U300 or glargine U100 at 80% of daily hospital dose. If previous basal bolus only therapy or contraindications to previous oral therapy, discharge on basal bolus at 100% of daily hospital dose.

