If any FBG or RBG 40- 69 mg/dl	Decrease by 8 IU or 20% of total daily dose
If any FBG or RBG < 40 mg/dl	Decrease total daily dose by 30 - 40%

V.g. Aim 2. Statistical Analysis:

V.g.1. Sample Size and Power Calculations: The primary endpoint in Aim 2 is difference in glycemic control (mean daily BG) after hospital discharge. Under the same assumptions for equivalence margin and BG variability as in Aim 1, we have the same sample size requirement (i.e. 78 subjects per group after 10% attrition). Accounting for 10% attrition rate, we would need 90 patients per treatment group (total # of patients to be recruited: 180 subjects, 90 per treatment group), to achieve >80% power.

V.g.2. Analysis of Primary Endpoint:

The primary endpoint in this study is glycemic control measured by mean daily BG concentration after hospital discharge. Secondary outcomes include rate of hypoglycemia during follow-up, change in HbA1c, body weight in kilograms, number of episodes of severe hyperglycemia, complications and emergency room visits or hospital readmissions at 12 weeks post-discharge. To analyze these outcomes, we will follow the same analytic strategy proposed for the secondary endpoints of Aim 1. We will first compare the primary outcome using two-sample t-tests (or Wilcoxon tests) or one-way ANOVA, followed by multivariate linear regression to estimate and test the difference between the two treatment groups while simultaneously accounting for other potential confounders. Transformations will be applied if normality violation is detected. Stepwise, backward, or forward model selection strategy will be adopted to determine the variables to be included in the final model. Standard diagnostic and model checking procedures will be applied to examine the fit of the developed models.

DATA HANDLING AND RECORD KEEPING:

Data collection records with personal identifiers will be stored in locked file cabinets. Presentation of the study results at regional or scientific meetings or in publications will not identify subjects. Access to research and confidential records will be limited to clinical investigators, research coordinators, and the IRB at Emory University.

All data will be entered electronically in Redcap by participating sites. Sponsor site expects data to be entered in Redcap within 10 days of phone call or outpatient visit.

VI. Methods and Procedures Applied to Human Subjects:

VI.a. Subject Population:

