Subjects with persistent hyperglycemia (≥ 2 glucose readings ≥ 400 mg/dL, ≥ 3 consecutive glucose readings > 280 mg/dL, or with a mean daily blood glucose concentration ≥ 280 mg/dL) and no treatable intercurrent cause for the hyperglycemia has been identified, will be considered as treatment failure and discontinued from the study. If needed, subjects will be started on continuous insulin infusion.

VII. Study Sites: This study will be performed at Grady Memorial Hospital, Emory University Hospitals, Atlanta, GA, Minneapolis Medical Research Foundation-Hennepin Medical Center, Minneapolis, and The Cleveland Clinic Foundation, Ohio.

VIII. CLINICAL MANAGEMENT GUIDELINES

VIII.a. Admission Laboratory Studies

Standard of care laboratory studies including glucose, HbA1C, and chemistry will be measured on admission and as determined by the treating physician.

For **research purposes** a blood sample will be obtained to measure HbA1C at 1 month and 3 months after discharge. In addition, a urine pregnancy test will be performed, when clinically indicated prior to randomization (in female subjects of child bearing potential only).

VIII.b. Assessment and Monitoring of Hospital Mortality

The investigators and research team will follow study subjects daily and the presumed cause of death will be recorded. Information on the attending physician’s summary of events surrounding subject’s demise will also be documented.

VIII.c. Assessment and Monitoring of Nosocomial Infections

Nosocomial infections will be diagnosed based on standardized CDC criteria (40). New nosocomial infections will not be diagnosed until 48 hours after study initiation to minimize the chance that the infection was actually present (but undiagnosed) prior to study initiation.

The investigators will review each subject’s records regarding potential new infection diagnosis daily on each weekday from Monday to Friday. Data from the weekends will be collected on the following Monday. The coded infection diagnosis and the presumed causative microorganism will be determined daily on a Monday to Friday basis, with weekend data entered on the following Monday.

Aim 1. Inpatient Arm – Flow Chart

Visit Type	Hosp- Day 1	Hosp- Day 2	Hosp- Day 3	Hosp- Day 4	Hosp- Day 5	Hosp- Day 6	Hosp- Day 7	Hosp- Day 8	Hosp- Day 9	Hosp- Day 10
Visit #	1	2	3	4	5	6	7	8	9	10
Time-days	1	2	3	4	5	6	7	8	9	10
Inf. consent	x									
Inclusion/excl criteria	x									
Randomization	x									

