Withdrawal criteria	x	x	x	x	x	x	x	x	x	x
Dose adjustment		x	x	x	x	x	x	x	x	x
Efficacy										
Vital signs ¹	x									x
Phys Exam ¹	x									x
Body weight	x									x
BMI	x									x
HbA1c	x									
Fasting BG	x	x	x	x	x	x	x	x	x	x
Pre-meal BG	x	x	x	x	x	x	x	x	x	x
Safety										

Adv events	x	x	x	x	x	x	x	x	x	x
Hypoglycemia	x	x	x	x	x	x	x	x	x	x
Urine pregnancy test	x									x
Trial material										
Drug dispense ²	x									

¹At time of study enrollment and hospital discharge ²As needed

Flow Chart: Aim 2, Outpatient Study

Visit Type	Hospital Day 1	TC	Clinic visit	TC	TC	TC	Clinic visit
Visit #	1	2	3	4	5	6	7
Time-wks	0	2	4	6	8	10	12
Inf. consent	x						
Incl/excl criteria	x						
Randomization	x						
Withdrawal criteria		x	x	x	x	x	x
Drug Compliance		x	x	x	x	x	x
Dose adjustment		x	x	x	x	x	x
Efficacy							
Vital signs	x		x				x
Phys Exam	x		x				x
Body wgt	x		x				x
BMI	x		x				x
HbA1c	x		x				x
Fasting BG	x		x				x
Safety							
Adv events	x	x	x	x	x	x	x
Hypoglycemia	x	x	x	x	x	x	x
Urine pregnancy test	x		x				
CMP or BMP	x		x				x
Trial material							
Drug dispense	x		x				
Drug account	x		x				x

IX. Potential Risks to the Subject:

IX.a. Hypoglycemia. It is possible that following the proposed protocol, patients receiving insulin glargine U300 and U100 may develop hypoglycemia. The risk of hypoglycemia in non-ICU patients treated with subcutaneous insulin is between 5–30% (12, 17, 41, 42). The number of hypoglycemia will be analyzed statistically. For the purpose of this analysis, hypoglycemia is defined as a BG < 70 mg/dL. Severe hypoglycemia is defined as BG < 40 mg/dL.

X. Protection against risks:

We will follow safeguards to minimize the risk to our subjects: a) we will carefully monitor capillary BG at the bedside using a hand-held glucose meter, b) only experienced nurses/or phlebotomist will draw blood samples, and c) women of reproductive age who are sexually active will undergo a urine pregnancy tests prior to participation in the study. To prevent significant clinical events, no patients with history of significant liver, renal impairment or cardiac failure will be recruited in this study.

X.a. Hypoglycemia: We expect that approximately 10% in the inpatient setting and ~20% in the outpatient (post-discharge) arm will experience one or more episodes of hypoglycemia. To minimize the risk of hypoglycemia, the starting dose will be reduced in the basal bolus insulin regimen (TDD: 0.3 units

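### The plan does not settle whether Aim 2 consent comes before or after open-label allocation, and its Aim 2 analysis would not reliably protect the comparison from entry or loss that differs by arm

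*Combined protocol and SAP*

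**What the plan says.** The Specific Aims and section V.b describe the source of Aim 2 in the same words: patients with HbA1c of at least 7.5% "enrolled in Aim 1 will be invited to participate in this open label prospective outpatient study". Neither gives a time for the invitation. Section V.b adds that patients with admission HbA1c below 7.5% "will be discharged on their preadmission antidiabetic regimen and will not be included in the Aim 2 outpatient study".

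The table headed "Flow Chart: Aim 2, Outpatient Study" ticks informed consent, eligibility and randomization at visit 1, labelled "Hospital Day 1", week 0. The Aim 1 flow chart also puts consent and randomization on hospital day 1.

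Section IV.e states: "This is an open label randomized controlled trial". It describes one 1:1 allocation, in blocks based on prior insulin use. No section describes a second allocation for Aim 2.

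Under the Treatment Failure Criteria, patients with persistent hyperglycemia "will be considered as treatment failure and discontinued from the study". Section VI.d lets the investigator withdraw patients for safety or non-compliance.

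On analysis, section V.g.2 says: "We will first compare the primary outcome using two-sample t-tests (or Wilcoxon tests) or one-way ANOVA". A multivariate linear regression follows, with covariates chosen by stepwise, backward or forward selection. Section V.g.1 sizes Aim 2 on the Aim 1 margin and standard deviation.

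**The concern.** Aim 2 has its own primary endpoint and its own sample size, and it is planned as a comparison of the two insulins against a margin. That comparison is a randomized one only if membership of the Aim 2 groups does not depend on what happened after allocation.

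Inviting people who are already enrolled suggests a second decision. In an open-label trial, patient and investigator may by then know the arm and how the hospital stay went, including hypoglycemia and poor control. If willingness to continue differs by arm for those reasons, the two outpatient groups differ before the first outpatient glucose value is recorded.

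A second route does not depend on consent. A patient discontinued for treatment failure or withdrawn in hospital was randomized but has no outpatient outcome. Treatment failure is defined by glucose, the quantity that Aim 2 compares.

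The plan defines no Aim 2 analysis population. It also plans no count by arm of those eligible, invited, declining and entering.

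**Working it through.** **Timing: the texts side by side**

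| Place | What it fixes | What it leaves open |
|---|---|---|
| Specific Aims; V.b | Aim 2 comes from Aim 1 enrollees | When they are asked |
| Aim 2 flow chart | Consent and randomization at hospital day 1, week 0 | Whether this is the Aim 1 consent and allocation |
| V.d and Aim 2 chart | Clinic visits at 1 and 3 months after discharge, charted at weeks 4 and 12 | Week 0 therefore works as discharge, yet carries the label of hospital day 1 |
| IV.c | Inpatient glucose averaged over up to 10 days | Day 1 and discharge can be well apart |
| IV.e | One open-label allocation | What the randomization tick in the Aim 2 chart refers to |

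Two readings fit. In one, a single day-1 consent before allocation serves both aims. In the other, Aim 2 consent is taken later, possibly near discharge. The protocol text does not choose between them.

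**The plan's own figure**

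Inputs from sections IV.g and V.g.1: margin 18 mg/dl, SD 45 mg/dl, true difference 0, power 80%, one-sided test. Alpha is not stated; one-sided 0.05 is inferred because it reproduces the plan's number.

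n per arm = 2 × [45 × (1.645 + 0.842) / 18]² = 77.3, so 78. This agrees with the plan.

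Standard error of the difference = 45 × √(2/78) = 7.2 mg/dl.

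**Size of a bias from entry that depends on arm**

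These inputs are assumptions; the documents give none of them.

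- Let d be the proportion of eligible patients who decline, and g the mean glucose of decliners minus that of acceptors.
- If all eligible patients in an arm have mean m, the acceptors have mean m − d × g.
- With no true difference between arms, the observed U300 minus U100 difference is −(d for U300 − d for U100) × g.

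Take g = 30 mg/dl:

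- 30% decline on U300 and 10% on U100: −(0.20 × 30) = −6 mg/dl, and 6/18 = one third of the margin.
- A 5-point difference in declining: −(0.05 × 30) = −1.5 mg/dl, and 1.5/18 = 8% of the margin.
- Equal declining: 0.

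The sign is not known. If more U300 patients decline and decliners have lower glucose, as is plausible when hypoglycemia drives the decision, the shift goes against U300. It also reverses if declining is more frequent on U100.

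**What such a shift does to the test** (normal approximation, 78 per arm)

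- Shift in favour of U300, true difference at the margin. The one-sided 5% error becomes Φ(6/7.2 − 1.645) = about 21%, or Φ(1.5/7.2 − 1.645) = about 7.5%.
- Shift against U300, true difference zero. Power falls from about 80% to Φ(12/7.2 − 1.645) = about 51%, or Φ(16.5/7.2 − 1.645) = about 74%.

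**What does not cause bias**

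The 7.5% cut-off uses admission HbA1c, fixed before allocation. Restricting both arms to that subgroup keeps the comparison randomized.

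**The case against.** The strongest objection is to a reading that a reader might infer: that Aim 2 patients are in fact invited after randomization with the arm known, so that the outpatient groups have already lost the protection of randomization. The documents do not say this. The invitation wording names a source population, not a time, and the only explicit timing is the flow chart, at hospital day 1. Section XIV fits a single study: one payment schedule of $100 for the stay and $75 for each of two visits, total $250. The consent form was not available for this review and may settle the matter. If one consent before allocation covers both aims, selection through consent by arm does not arise. This stands, and the point is therefore conditional.

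It would also be wrong to say that Aim 2 is analysed without adjustment, since section V.g.2 plans a regression after the unadjusted test. What remains is that its covariates are chosen from the data, so the adjustment is not known in advance and cannot be relied on to correct for who entered.

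The figures of 1.5 to 6 mg/dl rest wholly on assumed values. That also stands: they show what is possible, not what is expected.

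Finally, earlier consent does not cure losses through treatment failure or withdrawal. That is correct. Those losses are a separate route and need their own remedy.

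**Conclusion.** The concern holds in conditional form. Text and flow chart leave the timing of Aim 2 consent relative to open-label allocation unreconciled. If the invitation follows allocation, entry can depend on the arm and on the inpatient course. Independently of that, treatment failures and withdrawals between allocation and outpatient follow-up can remove patients differently by arm. The planned analysis does not reliably guard against either.

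The size is unknown. The entry bias is 1.5 to 6 mg/dl, in either direction, against a margin of 18 mg/dl, if declining differs by 5 to 20 points and decliners differ from acceptors by 30 mg/dl. It is zero if entry does not depend on arm. The effect of failures and withdrawals was not quantified. The plan should be amended on this point because the remedy is cheap and selection by arm cannot be undone once it has occurred.

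**What to change.** 1. Reconcile the Specific Aims and section V.b with the Aim 2 flow chart: state that one consent, taken before allocation, covers both aims, and that Aim 2 carries forward the Aim 1 allocation.
2. Define the Aim 2 analysis set as all randomized patients with admission HbA1c of at least 7.5%, in their assigned arm.
3. Make the primary Aim 2 analysis a regression with fixed adjustment for admission HbA1c and prior insulin use (the randomization factor), in place of the unadjusted test and the stepwise selection. This adjustment does not by itself correct for selection on inpatient experience; items 1 and 2 address entry.
4. Report by arm how many were eligible, entered, declined or were discontinued, with reasons.
5. Add a missing-data sensitivity analysis for patients in the set without outpatient glucose. This addresses the failures and withdrawals that earlier consent cannot prevent.

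The cost is consent wording, a few sentences in section V.g.2, one participant-flow table and one sensitivity analysis. Some patients will consent to Aim 2 and then prove ineligible on HbA1c. The as-randomized set will include patients with missing outcomes, which the analysis must handle openly.

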Hypothesis: Treatment with glargine U300 will result in equivalent glycemic control in hospitalized patients with T2D. Glargine U300 will result in lower number of hypoglycemia compared to glargine.

Aim 2: To determine differences in glycemic control after hospital discharge between treatment with glargine U300 and glargine U100 in medicine and surgery patients T2D. Patients with poorly controlled diabetes ($HbA1c \geq 7.5\%$) enrolled in Aim 1 will be invited to participate in this open label prospective outpatient study. The total duration of the study is 3 months. Patients with an $HbA1c$ between 7.5% and 10% will be discharged on preadmission oral antidiabetic agents plus glargine U300 and U100 once daily. Patients with an admission $A1C \geq 10\%$ will be discharged on basal bolus regimen with glargine and glulisine insulin before meals.

Hypothesis: treatment with glargine U300 and U100 will result in a similar improvement in HbA1c levels after hospital discharge. Glargine U300 will result in lower number of hypoglycemia compared to U100.

II. BACKGROUND AND CURRENT STATUS OF WORK IN THE FIELD.

Inpatient glycemic control in non-ICU setting. A large body of evidence has shown that in hospitalized patients, the presence of hyperglycemia and diabetes is associated with increased risk of complications and death (1-6, 28-31). Several randomized multi-center trials have shown that the use of basal bolus insulin regimen result in improved glycemic control and reduced rate of hospital complications compared to sliding scale regular insulin (SSI) in patients with T2D (12-14). We have reported that treatment with basal and basal bolus regimens using glargine U100 results in greater improvement in BG control and a reduction in the frequency of hospital complications including postoperative wound infection, pneumonia, bacteremia, and acute renal and respiratory failure compared to SSI treatment.(16, 17, 32, 33) In addition, the use of basal bolus regimen with glargine U100 is safe with low rate of hypoglycemic events. Based on these studies and others, clinical practice guidelines for the management of hyperglycemia in non-ICU setting have favored the use of basal prandial insulin regimens with insulin analogs for most inpatients with T2D (6, 19, 31).

Efficacy and safety of new glargine U-300 insulin:

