- Patients on oral agents plus basal insulin (NPH, glargine, detemir) prior to admission with HbA1C between 7.5% and <10% will be discharged on their oral agents plus glargine U300 or glargine U100 at 50% of daily hospital dose.
- Patients on oral agents plus basal insulin (NPH, glargine, detemir) prior to admission with an admission A1C ≥ 10% will be discharged on their oral agents plus glargine U300 or glargine U100 at 80% of daily hospital dose. If contraindications to previous oral therapy, discharge on basal bolus at 100% of daily hospital dose.

Patients treated with basal or basal bolus regimen prior to admission will be discharged on 50%-80% of their preadmission TDD with glargine once daily and glulisine before meals.

Concomitant Medications:
Background medications:

Metformin. Metformin is considered background medication (non-investigational medicinal product) and will not be provided during the trial. The total daily dose of metformin prior to admission will be restarted at hospital discharge with no dose adjustments occurring during the trial. Patients with eGFR between 30-45 ml/min will be discharged at a max-dose of 500 mg twice daily. Patients with eGFR < 30 ml/min will not be allowed to receive metformin.

Sulfonylurea and Insulin secretagogues. Sulfonylurea treatment is considered background medication (non-investigational medicinal product) and will not be provided during the trial. The total daily dose of sulfonylurea prior to admission will be reduced by 50% or stopped at hospital discharge at the investigator's discretion.

Pioglitazone. Pioglitazone is considered background medication (non-investigational medicinal product) and will not be provided during the trial. The total daily dose of pioglitazone prior to admission will be restarted at hospital discharge. No dose adjustment or up-titration will occur during the trial; however, in the event of peripheral edema or signs of volume overload, the dose of pioglitazone can be reduced or stopped at the investigator's discretion.

DPP4-inhibitors. DPP4-i treatment is considered background medication (non-investigational medicinal product) and will not be provided during the trial. The total daily dose of DPP4-I will be adjusted as per renal function (eGFR). No dose adjustment or up-titration will occur during the trial.

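### Discharge rules for Aim 2 patients with HbA1c of 10% or more conflict between the Specific Aims and Section V.b, and again within V.b

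*Combined protocol and SAP*

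**What the plan says.** Two parts of the combined protocol and SAP set the discharge treatment for Aim 2.

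- **Specific Aims, Aim 2.** Patients with an admission HbA1c of 10% or more "will be discharged on basal bolus regimen with glargine and glulisine insulin before meals". No exception is made for prior treatment, and no dose is given.
- **Section V.b, oral agents.** At 10% or more, patients who came in on oral agents "will be discharged on their oral agents plus glargine U300 or glargine U100 at 80% of daily hospital dose". The same bullet adds: "If previous basal bolus only therapy or contraindications to previous oral therapy, discharge on basal bolus at 100% of daily hospital dose".
- **Section V.b, oral agents plus basal insulin.** The rule at 10% or more is the same, and basal bolus applies only if oral therapy is contraindicated.
- **Section V.b, no previous drug treatment.** These patients "will be discharged on 50% of daily basal insulin (glargine U300 or glargine U100) hospital dose". No HbA1c cut-off is attached.
- **Section V.b, closing line.** Patients previously on basal or basal-bolus insulin "will be discharged on 50%-80% of their preadmission TDD with glargine once daily and glulisine before meals". Again there is no HbA1c limit.

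No text says which rule takes precedence. The figure at the start of Section V is not visible in the copy reviewed. It may show what was intended, but the written rules would still disagree.

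**The concern.** There are two separate contradictions.

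The first is between the Aims and V.b. For a patient at 10% or more who was untreated, on oral agents, or on oral agents plus basal insulin, the Aims prescribe mealtime insulin at home. V.b withholds it unless an exception applies.

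The second lies inside V.b and does not depend on the Aims. A patient whose previous therapy was basal bolus only, with HbA1c of 10% or more, meets both the full-hospital-dose clause and the closing line. The two differ in percentage and in base: one uses the hospital dose, the other the preadmission dose.

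A site cannot follow both rules for one patient. The choice decides whether the patient has mealtime insulin at home and how much insulin in total. The first scheduled contact is a telephone call at week 2 (V.d and the Aim 2 flow chart), so a dose that is too high or too low can stand for two weeks. Section V.e also collects protocol adherence, which cannot be scored when two instructions apply.

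**Working it through.** The plan states no figure on this point, so there is none to reproduce. The check is a comparison of rules and then of doses.

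**Step 1. Rules side by side, HbA1c of 10% or more**

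| Prior treatment | Specific Aims | Section V.b |
|---|---|---|
| None | basal bolus | 50% of hospital basal dose, no mealtime insulin |
| Oral agents | basal bolus | oral agents + glargine at 80%; basal bolus at 100% under the exceptions |
| Oral agents + basal insulin | basal bolus | oral agents + glargine at 80%; basal bolus at 100% if oral therapy is contraindicated |
| Basal bolus only | basal bolus | 100% of hospital dose **and** 50% to 80% of preadmission total |

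**Step 2. Size of the conflict inside V.b**

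Inputs:

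- The hospital start as a fraction H of the preadmission total daily dose (TDD). Section IV.f gives "Randomization BG <200mg/dl-give 80% of the TDD" and "Randomization BG>200mg/dl-give 100% of the TDD", so H = 0.8 or 1.0. Section IV.d (Basal Bolus Insulin Protocol) and Section X.a mention only the 20% reduction, so H = 0.8.
- Rule A, the clause in the oral-agent bullet: 1.00 × H.
- Rule B, the closing line: 0.5 to 0.8.

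Ratio A/B before any inpatient adjustment:

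- H = 0.8: 0.8/0.8 = 1.0 to 0.8/0.5 = 1.6
- H = 1.0: 1.0/0.8 = 1.25 to 1.0/0.5 = 2.0

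**Step 3. Effect of inpatient adjustment (illustrative paths, assumed)**

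Section IV.f fixes the starting split: "Half of TDD will be given as basal (glargine U300 or U100) and half as rapid-acting insulin". Daily increases act on the basal half. A cut for hypoglycemia acts on the whole dose.

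- Three daily basal increases of 20%: H × (0.5 × 1.2³ + 0.5) = H × 1.364, which is 1.091 or 1.364. The ratio is 1.36 to 2.18, or 1.70 to 2.73.
- One 20% cut: H × 0.8 = 0.64 or 0.80. The ratio is 0.80 to 1.28, or 1.00 to 1.60.

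Across these paths the ratio runs from 0.8 to 2.7. The starting-dose ratios therefore show that the rules disagree. They do not predict an individual's discharge dose.

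**Step 4. Effect on the arm comparison**

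Assume hypoglycemia in 30% on oral agents plus basal insulin and 40% on basal bolus. These are approximate rates from the earlier discharge study described in Section II, where regimens were assigned by HbA1c. Suppose basal-bolus use differed by 10 percentage points between arms. The induced difference would be 0.10 × (40 − 30) = 1 point. With 78 per arm (V.g.1), the standard error of the arm difference is √(2 × 0.3 × 0.7/78) = 0.073, or 7.3 points. At the roughly 20% outpatient rate expected in X.a it is √(2 × 0.2 × 0.8/78) = 0.064, or 6.4 points. Either way the shift is small beside the sampling error.

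**The case against.** The Aims text is a summary without doses, and V.b is the only text from which a dose can be written. Most sites would follow V.b. That is a fair answer to the first contradiction, which then needs only one corrected sentence. It does not answer the second, where both rules stand in V.b.

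The full-dose clause sits inside a bullet about patients on oral agents, so its reach is unclear. This is also fair. But the clause names previous basal-bolus-only therapy, and the closing line names prior basal-bolus patients without an HbA1c limit, so such patients at 10% or more are covered by both.

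A reader might infer more than the documents support:

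- **A general twofold dose gap.** The 2.0 needs the 100% start in IV.f. On IV.d and X.a the ceiling is 1.6. With an 80% start and the 80% discharge option the two doses coincide.
- **A fourfold gap for untreated patients.** V.b gives them 0.5 × 0.5 = 25% of the hospital total at the starting split. A fourfold gap follows only if the Aims mean basal bolus at 100%, and the Aims give no dose. At an assumed 50% it would be twofold.
- **That the unqualified 50% and 80% glargine rules mean total daily insulin.** The earlier algorithm in Sections II and III points that way. V.b's rule for untreated patients explicitly uses the basal dose. At the starting split the choice of base doubles or halves the glargine dose, so it should not be settled by inference.
- **That the 50% to 80% range is itself a defect.** It is ordinary clinical latitude. The fault is the overlap with another rule.

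V.b tailors treatment by prior therapy and HbA1c on purpose, so a mixture of discharge regimens is no error. Patients also receive meters, logbooks and hypoglycemia training (V.c), which softens the two-week gap.

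**Conclusion.** The contradiction is real and should be corrected. At HbA1c of 10% or more, the Aims and V.b disagree on mealtime insulin for three prior-treatment groups. V.b also gives prior basal-bolus patients two doses, differing before adjustment by 1.0 to 1.6 times (80% start) or 1.25 to 2.0 times (100% start).

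The consequence is inconsistent dosing, with hypoglycemia or hyperglycemia risk in the two weeks before first contact. A reader might infer that the Aim 2 comparison is biased. The documents do not support that. The rules are the same for both arms, and randomization is blocked on prior insulin use. Open-label staff could apply the rules differently by arm, but under the assumptions above even a 10-point imbalance moves the hypoglycemia difference by about 1 point.

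The documents do not say how many patients fall in each group, so the number affected cannot be estimated.

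**What to change.** 1. In the Specific Aims, replace the sentence on HbA1c of 10% or more with a reference to Section V.b.
2. In V.b, move the rule for previous basal-bolus-only therapy at 10% or more out of the oral-agent bullet, and state that only one rule applies to these patients. The default would be the specific rule (full hospital dose), with the 50% to 80% line limited, for prior basal-bolus patients, to HbA1c from 7.5% to below 10%. Because the specific rule is usually the higher dose, the sponsor should confirm it on clinical grounds. Patients on basal insulin without oral agents should stay under the closing line, so that none is left without a rule.
3. Ask the sponsor to state whether the unqualified 50% and 80% glargine percentages refer to the basal or the total hospital dose.
4. Report discharge regimen and starting dose by arm, from the insulin dosage and oral-agent data already collected under V.e.

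The cost is one sentence in the Aims, a few lines in V.b, a clinical decision by the sponsor and a notice to the sites. Patient numbers, visits, sample size and tests do not change.
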